## 2. STATISTICAL HYPOTHESES

There is no formal research hypothesis that will be statistically tested in this study.

### 2.1. Multiplicity Adjustment

- There is no multiplicity adjustment requirement.

## 3. ANALYSIS SETS

For analyses purposes, the following populations are defined:

Analysis Set	Definition / Criteria	Analyses Evaluated
Screened	
 
• All participants who were screened for eligibility
 
	
 
• Study Population
 

Enrolled	
 
• All participants who entered the study (who received study intervention or underwent a post-screening procedure)
 
• NOTE: screening failures (who never passed screening even if re-screened) and participants screened but never enrolled into the study (Met eligibility but not needed) are excluded from the Enrolled Analysis set as they did not enter the study.
 
	
 
• Study Population
 

Assigned	
 
• All participants who were assigned to study intervention in the study.
 
	
 
• Study Population
 

Safety	
 
• Participants who received study intervention.
 
	
 
• Safety
 

Pharmacokinetic (PK)	
 
• All participants in the safety analysis set who had at least 1 non-missing PK assessment (Non-quantifiable [NQ] values will be considered as non-missing values).
 
	
 
• PK
 

CONFIDENTIAL

Analysis Set	Definition / Criteria	Analyses Evaluated
	
 
• Data will be reported according to the actual study intervention.
 
	

## 4. STATISTICAL ANALYSES

### 4.1. General Considerations

Schedule of activities are outlined in protocol section 1.3.

#### 4.1.1. General Methodology

Participants who prematurely withdrew from study may be replaced at the discretion of the sponsor if they were not discontinued due to AEs or SAEs.

Data will be listed and summarized for each cohort of the study according to GSK reporting standards wherever applicable. Unless otherwise specified, descriptive summaries for untransformed continuous variables will include n, mean (95%CI; PK parameters only), standard deviation (SD), CV% (PK parameters only), median, minimum, and maximum. For Tmax, only median, minimum and maximum will be reported. CI and CV% will not be reported for safety summaries. Parameters which are log-transformed prior to analysis will be summarized using n, geometric mean (95% CI), SD (Log), geometric between subject CV (CVb%) and arithmetic mean (95% CI), SD, median, minimum, and maximum. For the geometric ratio and mean difference, a 90% CI will be presented. Categorical data will be summarized as number and percentage of participants in each category.

All data displays will follow the GSK integrated data standards library (IDSL) display standards. Final analyses will be performed after the completion of the study and final dataset authorization.

#### 4.1.2. Baseline Definition

For all endpoints the baseline value will be the latest pre-dose assessment with a non-missing value, including those from unscheduled visits. If time is not collected, Day 1 assessments are assumed to be taken prior to first dose and used as baseline.

Unless otherwise stated, if baseline data is missing no derivation will be performed and baseline will be set to missing.

CONFIDENTIAL

## 4.2. Primary Endpoint(s) Analyses

### 4.2.1. Definition of endpoints

Pharmacokinetic analysis will be performed by or under the direct auspices of Clinical Pharmacology Modelling & Simulation, GSK. Pharmacokinetic parameters will be calculated by standard **CCI** analysis according to current working practices and using the currently supported version of *Phoenix WinNonlin*. All calculations of **CCI** parameters will be based on actual sampling times. Pharmacokinetic parameters listed will be determined from the plasma concentration-time data, as data permits.

Parameter	Parameter Description
AUC (0-∞)	
Area under the concentration-time curve from time zero extrapolated to infinity, using the linear trapezoidal rule for each incremental trapezoid and the log trapezoidal rule for each decremental trapezoid.
 
<math>AUC_{(0-\infty)} = AUC_{(0-t)} + C_{(t)}/\lambda_z</math> where <math>C_{(t)}</math> is the last quantifiable concentration and <math>\lambda_z</math> is terminal phase elimination rate constant.
 
<math>AUC_{ex} = \text{The percentage of } AUC_{(0-\infty)} \text{ obtained by extrapolation } (\%AUC_{ex})</math> will be calculated as:
 $(\text{AUC}_{(0-\infty)} - \text{AUC}_{(0-t)}) / \text{AUC}_{(0-\infty)} \times 100$ 
It is acceptable to include data from profiles with >20% extrapolated as long as at least 80% of the profiles in the study have <20% of the <math>AUC_{(0-\infty)}</math> as extrapolated area. It is unacceptable to use <math>AUC_{(0-\infty)}</math> data if >40% of the AUC has been extrapolated.

C max	Maximum observed concentration, determined directly from the concentration-time data.

### 4.2.2. Main analytical approach

The primary PK analyses will be based on the PK Analysis Set unless otherwise specified. Plasma camlipixant concentration-time data will be listed for each participant and standard summary statistics will be calculated (i.e. N [number of subjects in the cohort), n [number of evaluable values), No. imputed [number of values imputed), arithmetic mean, 95% CI, standard deviation, CV%, median, minimum and maximum) by cohort (healthy versus hepatic impairment group) and planned sampling time.

Individual, mean and median plasma camlipixant concentration-time profiles will be plotted for each cohort on both linear and log-linear scales. A reference line indicating the lower limit of quantitation (LLOQ) will be included in plots. For handling concentrations which are below the limit of quantitation (i.e. NQ, non-quantifiable) the following will be applied:

**CONFIDENTIAL**

For plasma concentration data, concentrations below the limit of quantification (NQs) at the beginning of a participant profile (i.e. before the first incidence of a measurable concentration) will be assigned to be zero. For NQs at the end of the participant profile (i.e. after the last incidence of a measurable concentration):

- for individual plots and pharmacokinetic analyses, these will be dropped (set to missing)
- for summary statistics, these will be set to 0
- Individual NQs which fall between 2 measurable concentrations will be set to missing

*Strategy for Intercurrent (Post-Randomization) Events*

Issues that affect exposure to study drug such as emesis, dosing errors, or important protocol violations will be handled with an on-treatment strategy i.e., use available data up until the intercurrent event. Interest lies in estimating the effect of HI on the PK of camlipixant, when patients receive the single dose of camlipixant and while patients are sufficiently compliant with camlipixant to accurately assess exposure.

*Strategy for Missing Data*

No Sample (NS), No Result, i.e. lost sample (NR), Insufficient Sample (IS) and Not Analyzed (NA) are truly missing and should be set to missing for reporting including summary statistics and graphical presentation.

**4.2.2.1. Statistical Analyses / Methods**

After log transforming PK parameters  $AUC_{(0-\infty)}$  and  $C_{max}$  for camlipixant, they will be analyzed using a mixed effects model with the cohort included as a fixed effect and a matching variable (indicating the matching of each healthy participant for each impairment participant) as a random effect. This matching variable will be categorical taking values 1, ...., k where k is the total number of matched sets.

*Statistical Methodology Specification:*

Endpoint / Variables

 
• Log transformed <math>AUC_{(0-\infty)}</math>, and <math>C_{max}</math> for camlipixant plasma concentrations. If there is not sufficient data to analyze <math>AUC_{(0-\infty)}</math> with a linear model, then <math>AUC_{(0-t)}</math> will be calculated and analyzed.
 

Model Specification
CCI

**CONFIDENTIAL**

CCI

**Subgroup Analyses**

- Not applicable.

**Sensitivity and Supportive Analyses**

- Not applicable.

Summary statistics (arithmetic mean, geometric mean, median, 95% CI [arithmetic and geometric], SD [arithmetic and on ln-scale], minimum, maximum, and CVb% [SQRT (exp (SD) – 1) x 100]) for plasma camlipixant PK parameters will be summarized by cohort.

### **4.3. Secondary Endpoints Analyses**

#### **4.3.1. Secondary endpoints**

##### **4.3.1.1. Definition of endpoints**

*Safety Endpoints:*

- Incidence of AEs, SAEs, AESIs.
- Incidence of participants with clinically relevant changes in clinical laboratory tests, ECG and vital signs assessments.

**CONFIDENTIAL****PK Endpoints:**

Pharmacokinetic parameters will be calculated by standard CCI ██████████ analysis according to current working practices and using the currently supported version of *Phoenix WinNonlin*. All calculations of CCI ██████████ parameters will be based on actual sampling times. Pharmacokinetic parameters listed will be determined from the plasma concentration-time data, as data permits.

Parameter	Parameter Description
t 1/2	Apparent terminal phase half-life calculated as: $t_{1/2} = \ln 2 / \lambda_z$
CL/F	Apparent clearance calculated as: CL/F=Dose/AUC (0-∞) If AUC (0-∞) cannot be accurately estimated, CL/F and Vz/F will not be calculated.
T max	Time of occurrence of C max , determined directly from the concentration-time data.
Vz/F	Apparent terminal phase volume of distribution calculated as: Vz/F=(CL/F)/ λ z

**NOTES:**

- Additional parameters may be included as required.

**4.3.1.2. Main analytical approach****Safety Analysis:**

All safety analyses will be performed on the Safety Analysis Set.

Analyses related to safety endpoints (AEs, ECGs, vital signs, and clinical laboratory tests) are described in [section 4.5](#).

**PK Analysis:**

Summary statistics will be summarized by cohort based on the PK Analysis Set. For Tmax, only median, minimum and maximum will be generated. For t1/2, CL/F, and Vz/F, the summary statistics specified for log transformed data (Section 4.1.1) will be generated.

CCI

**CONFIDENTIAL**

CCI

#### 4.4.2. Main analytical approach

##### PK Endpoints:

Summary statistics for exploratory plasma and urine PK parameters described in Section 4.4.1 will be summarized as appropriate based on the PK Analysis Set.

CCI

CCI

CCI

CCI

CCI

CCI

The relationship between camlipixant PK parameters and measures of HI (e.g., bilirubin, albumin, Child-Pugh score) may be examined in an exploratory manner via a linear regression approach or other appropriate methods.

**CONFIDENTIAL***Strategy for Missing Data:*

No Sample (NS), No Result, i.e. lost sample (NR), Insufficient Sample (IS) and Not Analyzed (NA) are truly missing and should be set to missing for reporting including summary statistics and graphical presentation. In case of one or more NQ data they will be assigned a value of zero concentration.

## **4.5. Safety Analyses**

The safety analyses will be based on the Safety Analysis Set, unless otherwise specified.

Safety endpoints that are included as secondary endpoints are included in [section 4.3](#).

### **4.5.1. Extent of Exposure**

A listing of study drug exposure data will be produced on Safety Analysis Set.

### **4.5.2. Adverse Events**

The definitions of AE, treatment-emergent AE (TEAE), SAE refer to section 10.3 of protocol.

AEs will be coded using the most current version 27.0 of Medical Dictionary for Regulatory Activities (MedDRA). A by participant AE, SAE and AESI data listing including verbatim term, coded term, treatment, severity (mild, moderate and severe), and relationship to treatment will be provided. A listing of taste AE questionnaire will be provided for any participants who spontaneously reports a taste disturbance AE.

Summary of incidence of AEs, SAEs and AESIs will be tabulated by system organ class (SOC) and preferred teams (PT) for each cohort.

An overview summary of AEs, including counts and percentages of participants with any AE, TEAEs, treatment-related TEAE, severe TEAE, treatment-related severe TEAE, death due to TEAE, TEAE caused study discontinuation, SAEs, treatment-related SAEs, Fatality and any AESI will be produced by cohort.

The number of participants reporting the TEAEs and the number of TEAEs reported will be summarized for each cohort. Separate summary tables including all AEs by maximum severity, treatment-related AEs, AEs caused study discontinuation, SAEs, and AESI will be generated as well. These summary tables will be presented by SOC and PT. In summary tables which are presented by SOC and PT, SOCs will be sorted in descending order of the total incidence then alphabetically, PTs will be sorted in descending order of the total incidence then alphabetically within the SOC. For the calculations in tables by maximum severity, each participant's AEs will be counted once under the maximum severity. For the calculations in tables by relationship to study treatment, each participant's AEs will be counted once under treatment-related.

**CONFIDENTIAL**

If treatment relationship and severity of AEs are missing, no imputation will be performed.

The definition of TEAE and AESI are described in Section 10.3.6 and Section 8.4.4 of the protocol, respectively.

#### **4.5.2.1. Cardiovascular Events**

The definition of cardiovascular events refers to Section 10.3.5 of protocol.

Listings of cardiovascular events assessment (including abnormal physical exams) and CV status will be provided.

### **4.5.3. Additional Safety Assessments**

#### **4.5.3.1. Laboratory Data**

Laboratory summaries will be presented by cohort. Absolute values and change from baseline in laboratory parameters will be summarized with descriptive statistics by timepoint. All laboratory data related to chemistry, hematology, urinalysis and other laboratory characters will be listed separately for participants. A listing will be produced including laboratory data with character results. Shift tables describing out of reference range shifts will be provided for clinical laboratory (hematology and chemistry) results.

Liver function laboratory tests and pregnancy tests (for female only) will be included with chemistry lab tests.

##### **4.5.3.1.1. Liver Events**

Liver monitoring reporting will be listed. The liver monitoring criteria are described in the protocol Section 7.1.1.

#### **4.5.3.2. ECG Data**

ECG values will include measurements of heart rate, PR, QRS, uncorrected QT, and QTcF intervals. ECG data summaries will be reported by cohort. Absolute values and change from baseline will be summarized with descriptive statistics by timepoint for ECG values. A separate summary table of ECG findings will be created. All ECG values and all ECG findings will be listed separately.

#### **4.5.3.3. Vital Signs Data**

Vital signs data summaries will be reported by study treatment. Vital sign assessments will include systolic and diastolic blood pressure, pulse rate, respiratory rate, and temperature. Absolute values and change from baseline over time in vital signs will be summarized with descriptive statistics by timepoint. All vital signs data will be listed.

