Source data	
All information in original records and certified copies of original records of clinical findings, observations, or other activities in a clinical study necessary for the reconstruction and evaluation of the study. Source data are contained in source documents (original records or certified copies).

Study intervention	
Term used throughout the clinical study to denote a set of investigational product(s) or marketed product(s) or placebo intended to be administered to a participant.
 
Note: “Study intervention” and “study treatment” are used interchangeably unless otherwise specified.

Study completion date	
The date on which the last participant in a clinical study was examined or received an intervention/treatment to collect final data for the primary outcome measures, secondary outcome measures, and AEs (that is, the last participant's last visit or LSV).

Study monitor	
An individual assigned by the sponsor and responsible for assuring proper conduct of clinical studies at 1 or more investigational sites.

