6.3. Blinding

This is an open-label study and all participants will be receiving the same 50 mg dose. The severe hepatic impaired group (Group 4) and the matched healthy controls (Group 5) may receive a reduced dose of 25 mg in Scenario 3 based on the review of safety and PK data in Part 1. The dose used in Group 4 and Group 5 will be communicated to the site prior to the start of screening.

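### SAP 4.5.3.3 groups the vital-signs summaries by study treatment instead of by cohort, which as written mixes hepatically impaired participants with their same-dose controls

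*SAP*

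**What the plan says.** SAP section 4.5.3.3 sets the grouping for vital signs: "Vital signs data summaries will be reported by study treatment". It then defines the content of those summaries: "Absolute values and change from baseline over time in vital signs will be summarized with descriptive statistics by timepoint". The section also provides for a listing of all vital signs.

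The rest of the SAP groups differently:

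- General rule, section 4.1.1: "Data will be listed and summarized for each cohort of the study according to GSK reporting standards wherever applicable".
- Adverse events, section 4.5.2: "The number of participants reporting the TEAEs and the number of TEAEs reported will be summarized for each cohort".
- Laboratory data, section 4.5.3.1: "Laboratory summaries will be presented by cohort".
- ECG, section 4.5.3.2: "ECG data summaries will be reported by cohort".

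The protocol's Definition of Terms says that study intervention and study treatment "are used interchangeably unless otherwise specified". On dose, protocol section 6.3 says: "This is an open-label study and all participants will be receiving the same 50 mg dose". It goes on to allow 25 mg in Scenario 3 for the severe HI group and its matched controls. Protocol section 4.1 and SAP section 1.2 confirm that, if the severe HI dose is reduced, the controls matched to that group take the reduced dose too.

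**The concern.** In many trials treatment arm and cohort are the same thing, and the choice of word would not matter. Here cohorts are defined by hepatic function and treatment is a single drug, given at one dose or possibly two. Because matched groups share a dose, a table with one column per treatment has no column for HI and none for healthy controls.

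The secondary safety objective in SAP section 1.1 is a comparison of HI participants with healthy controls, and its endpoint names vital signs alongside laboratory tests and ECG. SAP section 4.3.1.2 refers to section 4.5 for these analyses, and 4.5.3.3 is the part of it that covers vital signs. Read literally, laboratory and ECG values are compared between impaired and healthy participants and vital signs are not. The table of potential clinical importance criteria in SAP section 6.2.1 has no vital-sign row, so no visible flag fills the gap. Neither the version history nor section 7 of the SAP gives a reason for treating vital signs differently.

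**Working it through.** **Inputs**

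- 8 participants in each HI group (Groups 1, 3 and 4), 8 in Group 2, and 8 to 16 in Group 5 (protocol section 9.5; SAP section 5).
- Each HI participant is matched to one healthy control (protocol section 4.2). In Scenario 2 only, one Group 5 control may serve both a mild and a severe HI participant (protocol Table 2).
- Matched groups receive the same dose; 25 mg is tied only to Scenario 3 (protocol sections 4.1 and 6.3).
- After the interim review, only severe HI enrols in Part 2, and controls to mild HI are not enrolled (SAP sections 4.6 and 7).

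**Check of the plan's own total.** 8 + 8 + 8 + 8 + 16 = 48, which agrees with the stated maximum enrolment of up to 48.

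**Columns if grouped by study treatment**

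| Scenario | Column | HI | Healthy | Total |
|---|---|---|---|---|
| 1: severe only in Part 2 | 50 mg | 8 + 8 = 16 | 8 + 8 = 16 | 32 |
| 2: mild and severe, same dose | 50 mg | 8 + 8 + 8 = 24 | 8 + (8 to 16) = 16 to 24 | 40 to 48 |
| 3: mild and severe both dosed, severe at 25 mg | 50 mg | 8 + 8 = 16 | 8 + 8 = 16 | 32 |
| 3: same | 25 mg | 8 | 8 | 16 |

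Every column in every scenario contains both HI and healthy participants. Grouped by cohort, Scenario 1 gives four columns of 8: moderate HI, its controls, severe HI, and its controls.

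**Dilution in the design now in force.** If a mean change occurs only in a subset of n participants and the other groups do not change, the pooled mean shows the fraction n/N of it.

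- Change confined to severe HI: 8/32 = 0.25.
- Change in all HI participants: 16/32 = 0.50.

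For illustration only, take a mean change of 10 mmHg, an assumed value that is not in the documents. The pooled column would show 10 × 0.25 = 2.5 mmHg or 10 × 0.50 = 5.0 mmHg, with no control column to set it against.

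SAP section 5 still gives Group 5 as 8 to 16. With 1:1 matching and no mild HI group, 8 is the consistent number. At the printed upper limit of 16 the column would hold 40, and the fractions would be 8/40 = 0.20 and 16/40 = 0.40.

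**The case against.** The strongest reply is that this is loose wording and no one will build the pooled table. Section 4.1.1 already sets a by-cohort rule. Protocol section 9.3.2.1 said adverse events would be summarised by treatment, and the SAP turned that into cohort, so the sponsor has used the first term to mean the second. The ECG section next to it is almost identical in form and says cohort. The protocol glossary equates two terms; it does not define table columns. The table shells are not in the documents, so what will be produced is unknown.

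The consequence is also modest. The vital-signs endpoint is the incidence of clinically relevant changes, not the mean change by timepoint. Clinically significant vital-sign findings can be recorded as adverse events and so reach tables that are by cohort. All values are listed, no hypothesis is tested, and no visible decision rule uses these means.

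Most of this stands, and it limits the weight of the point. It does not remove it. Section 4.1.1 applies wherever applicable, and a specific sentence normally overrides a general one, so a programmer who follows 4.5.3.3 would be right to pool. That the phrase is probably left over is a reason to correct it. A by-cohort table rebuilt later from the listings would not be the one the SAP specified.

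**Conclusion.** The concern holds. Section 4.5.3.3 is inconsistent with the SAP's general rule and with its other safety sections, and the grouping it states cannot separate HI from healthy participants under any scenario. That conclusion depends only on matched groups sharing a dose, which the documents state.

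The single column of 32, and the fractions 0.25 and 0.50, need more: that the sentence is followed literally, that each group has 8 participants, that the other groups show no change, and that the severe HI group and its controls receive 50 mg. The last is an inference. The scenario text is redacted, but SAP section 4.6 says the first criterion was met, protocol section 9.3.1.1 describes Scenario 1 as severe HI only, and 25 mg appears only under Scenario 3.

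The effect is confined to a descriptive secondary safety summary. Primary PK results and participant-level data are not affected. It should be corrected, but it does not threaten the trial's main conclusions.

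**What to change.** In SAP section 4.5.3.3, replace 'study treatment' with 'cohort', so that vital signs use the same cohorts as the laboratory and ECG summaries, as updated by SAP section 7. The sentence should not carry its own list of cohorts. Section 7 removes the mild HI cohort and renames the Part 2 controls, but it says nothing of the pooled healthy controls named in section 6.1, and a second list could fall out of step.

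The cost is one phrase in the SAP, with no new data, threshold or protocol amendment. If a table shell already follows the present wording it would need the same change; the documents do not show whether one does.
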